Subclinical Cardiovascular Disease in Psoriatic Disease

Principal Investigator

[name], MS, FAHA, FACC
Associate Professor of Medicine (Cardiology and Hematology)
The Center for the Prevention of Cardiovascular Disease
New York University School of Medicine
[name]
[name]
[contact]
[contact]
e-mail: [contact]

Study Investigators

[name]
Post-doctoral research Fellow
The Center for the Prevention of Cardiovascular Disease
New York University School of Medicine
[name]
[name]
[contact]
[contact]
e-mail: [contact]

1. Synopsis

Cardiovascular disease (CVD) remains the leading cause of death in the US. Five modifiable risk factors: smoking, hyperlipidemia, diabetes, hypertension and obesity, account for 50% of CVD mortality between the ages of 45 – 79.¹ These traditional cardiac risk factors dictate who to treat with primary prevention measures but do not take into account patient-specific disease states such as psoriatic disease including psoriasis and psoriatic arthritis, which predispose to chronic inflammation. Patients with psoriatic disease have an increased risk of atherosclerotic heart disease and myocardial infarctions compared to matched controls.² Studies are needed on how the chronic inflammation seen in psoriatic disease translates into the increased atherosclerotic and thrombotic risk and how treatment reduces this CVD risk.

2. Background and significance

Psoriatic disease which includes psoriasis and psoriatic arthritis are chronic inflammatory disease states which have been shown to increase the risk of cardiovascular mortality.³ Psoriasis has a prevalence of 2 to 3 percent, with a bimodal distribution affecting most those 30 – 39 and again between 50 – 69 years of age.⁴ Meta-analysis on the association of CVD with psoriasis have yielded an overall relative risk (RR) of 1.5 for ischemic heart disease.⁵ Young adults are at even higher relative risk (RR) higher risk, with a RR for myocardial infarction of 3.1 compared to age-matched controls.⁶ Confounding this relationship is the increased prevalence of metabolic syndrome, obesity, HTN and hyperlipidemia within the psoriatic population.⁵ Despite this, epidemiologic studies have noted the increased risk of CVD remains after adjustment for these traditional CVD risk factors.⁶

The mechanism(s) between psoriatic disease and CVD are still being characterized.⁷ The systemic inflammation is linked to the production of numerous inflammatory cytokines such as interferon – γ , tumor necrosis factor (TNF), IL-17 and IL-22 with an overall activation of the innate immune system response.⁸ Through systemic inflammation, the initial stages of atherosclerosis develop with upregulation of vascular endothelial adhesion molecules and leukocyte translocation, platelet activation and increased vessel wall permeability to lipoproteins and inflammatory mediators.⁹

There have been studies linking the earliest phases of atherosclerosis, endothelial dysfunction and psoriasis. Psoriatic patients have impaired flow-mediated dilation, increased arterial stiffness and increased carotid intima-media thickness.¹⁰ Biochemically, a variety of extracellular microparticles, involved in both endothelial cell and platelet activation are elevated in those with moderate to severe psoriasis.¹¹ Platelet activation in particular through measurement of platelet-derived microparticles and soluble P-selectin are increased in psoriasis and linked to psoriasis severity.¹²

While there have been studies evaluating the effects of psoriatic specific treatment on endothelial dysfunction, there is a lack of evidence on the use of medications typically used for the primary prevention of CVD within the psoriatic population.¹⁰ The goals of the proposed study are three fold: As a first step to assess endothelial dysfunction, we will assess vascular function in psoriasis patients through non-invasive ultrasound imaging and through a novel technique: direct analysis of endothelial cells with minimally invasive endothelial vein harvesting.¹³ As a second goal, we will assess thrombotic risk through platelet activation and platelet – endothelial interaction. Finally, as a third goal, we will assess in patients with moderate to severe psoriatic disease changes to the endothelial function and platelet activation over time with the use of 81mg of aspirin and/or 40mg of atorvastatin.

3. Specific Aims

- 3.1 To evaluate the association between moderate to severe psoriatic disease and measures of vascular function.
- 3.2 To evaluate the association between moderate to severe psoriatic disease and measures of thrombotic risk.
- 3.3 To understand how traditional medications used in CVD prevention such as aspirin and statins affect vascular function and thrombotic risk in those with moderate to severe psoriatic disease.

4. Research Design

4.1 Recruitment

We will recruit patients across the spectrum of psoriatic disease (includes psoriasis and psoriatic arthritis and age and sex matched health controls).

4.2 Inclusion/Exclusion Criteria for Psoriatic Patients

Inclusion Criteria

1. Group 1: Subjects with a history of moderate to severe psoriatic disease
2. Age ≥ 18 & < 90
3. Able and willing to provide written informed consent for the study

Exclusion Criteria

1. Unable to speak Spanish or English
2. Active smoking (within the past year)
3. Autoimmune, rheumatologic or inflammatory disease which are not psoriasis or psoriatic arthritis
4. Known active cancer receiving treatment
5. Pregnancy
6. Anemia (hemoglobin < 9 mg/dl) or thrombocytopenia (Platelet count < 75), or thrombocytosis (Platelet count > 600)
7. A history of severe bleeding or bleeding disorders
8. Current medication use which interact with either aspirin or atorvastatin
9. Chronic kidney disease (CrCl < 30 ml/min)
10. Congestive heart failure
11. Currently taking aspirin or a statin.
12. NSAID use within the past 48 hours

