5. RISKS

The potential risks of phlebotomy are pain, bruising, fainting, or small infection at puncture site. The procedure to perform endothelial vein harvesting is identically to the placement of an IV and routine phlebotomy blood draw. These risks are pain, bruising, fainting or small infection at the puncture site.

Sterile gloves and sterile wires are used to harvest the endothelial cells. The wires are advanced < 5 inches. Our lab is partnering with a lab experienced with this technique and has published extensively on the technique for many years¹⁴. In their experience patients complain only on the routine discomfort of the IV insertion. There is a theoretical risk of vein thrombosis. In our collaborators experience, in over 10 years of sampling, not one thrombosis has occurred. To minimize this risk, we will encourage arm mobilization post procedure. We will be using our collaborators protocols and their consent language to ensure adequate patient knowledge on the risks of the procedure and we will train extensively prior to carrying out this low risk minimally invasive procedure to harvest endothelial veins. There lab has also agreed to help mentor and guide us to help with the appropriate and safe procurement of endothelial cells when performing this testing on our initial subject cohort.

Regarding non-invasive imaging of vascular function, there are no known risks associated with taking ultrasound pictures. The cuff on the forearm and the "pins and needles" sensation may be uncomfortable for participants. At their request, the cuff will be deflated and any discomfort should disappear within a few seconds. There are no known risks to the arterial tonometry measurements.

Treatment risks:

Aspirin and atorvastatin are standard medications used for the primary prevention of CVD. Nevertheless, there are risks associated with being on aspirin for 2 weeks. Use of aspirin has known side effects, including stomach irritation, ulcers, heartburn, easy bruising, and minor or major bleeding. Thus, we are using the lowest clinically effective dose (81mg) and for a very short period of time.

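### The anemia exclusion in 4.2 and 4.3 is printed as hemoglobin below 9 mg/dl (0.009 g/dl), a limit that excludes nobody as written; the unit needs correcting

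*Combined protocol and SAP*

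**What the plan says.** The exclusion criteria for psoriatic patients (4.2, item 6) contain one combined laboratory criterion: "Anemia (hemoglobin < 9 mg/dl) or thrombocytopenia (Platelet count < 75), or thrombocytosis (Platelet count > 600". The list for healthy controls (4.3, item 7) repeats it in the same words. No other section restates the hemoglobin or platelet limits, gives them a different unit, or corrects them.

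Two neighbouring items matter for context. The renal criterion in the same list does carry a unit: "Chronic kidney disease (CrCl < 30 ml/min". Both lists also have a bleeding exclusion that needs no laboratory value: "A history of severe bleeding or bleeding disorders".

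On what follows enrolment, section 4.5.5 caps the baseline blood draw at 60 ml. Section 4.5.6 caps the total at 120 ml for those who also take part in the optional follow-up collection. Table 1 gives controls no follow-up blood draw. Section 4.5.2 describes offering aspirin, alone or with atorvastatin, to part of Group 1. Section 5 lists among aspirin's known effects "easy bruising, and minor or major bleeding".

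**The concern.** Hemoglobin in milligrams per decilitre runs into the thousands, so a cut-off of 9 in that unit cannot separate anemic people from anyone else. The number sits in an exclusion criterion, not in background text, and it is the only numeric definition of anemia in the plan.

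The limit helps decide who goes on to research blood collection and, in Group 1, who may be offered a drug for which the protocol itself lists bleeding. If staff apply the printed limit, nobody is excluded by the number. If they silently substitute another unit, enrolment follows a rule that the protocol does not state. An audit against the protocol then could not confirm that a given person was correctly included or excluded on this item.

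**Working it through.** The plan has no calculated figure to reproduce here. The check is a unit conversion and a comparison.

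**Inputs**
- Hemoglobin limit: below 9 mg/dl (4.2 item 6; 4.3 item 7).
- Platelet limits: below 75 and above 600, no unit (same items).
- Hemoglobin in living adults: about 3 to 18 g/dl. This is an assumption from outside the documents.

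**Step 1: convert the limit.** 1 g = 1,000 mg, so 9 mg/dl = 9 / 1,000 = 0.009 g/dl, or 0.09 g/l.

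**Step 2: convert the assumed range.** 3 × 1,000 = 3,000 mg/dl and 18 × 1,000 = 18,000 mg/dl.

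**Step 3: compare.** 3,000 / 9 ≈ 333 and 18,000 / 9 = 2,000. Every value in the range is at least 333 times the printed limit, so the result is insensitive to where the lower end of the range is set.

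**Step 4: test example values.** The last column shows only what the same number would do in g/dl. It is not a statement that this is the intended rule.

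| Hemoglobin (g/dl) | In mg/dl | Excluded as printed (< 9 mg/dl)? | Excluded if 9 were in g/dl? |
|---|---|---|---|
| 3 | 3,000 | No | Yes |
| 5 | 5,000 | No | Yes |
| 7 | 7,000 | No | Yes |
| 8.9 | 8,900 | No | Yes |
| 12 | 12,000 | No | No |
| 15 | 15,000 | No | No |

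The printed unit therefore differs by a factor of 1,000 from one in which the same number would operate.

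**Step 5: platelet limits.** Take a count of 250 × 10^9/l, which is 250,000 per microlitre. In units of 10^9/l, 250 lies between 75 and 600 and the person is eligible. Per microlitre, 250,000 exceeds 600 and the person is excluded. The unit decides the result, and it is not printed. However, the limits are labelled "thrombocytopenia (Platelet count < 75" and "thrombocytosis (Platelet count > 600", so an ordinary count must fall between them. Of the two units tested, only 10^9/l (thousands per microlitre) allows that.

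**The case against.** The strongest reply is that this is a clerical slip with little practical effect. The criterion opens with the word anemia and puts the number in brackets. Section 4.3 has clinic patients identified by their own health care professional, and no clinician would take the item as admitting a severely anemic person. The separate exclusion for bleeding history works without any laboratory unit, and interacting medication and recent NSAID use are also excluded. No statistical quantity depends on the limit.

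Most of that stands, and it keeps the point small. It does not make the printed limit correct. A bleeding history is not a measure of current anemia. Section 4.3 also recruits through fliers and online postings, for which no such prior identification by a clinician is described.

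A reader might infer more than the documents support:
- **That the platelet limits fail in the same way**, excluding nobody at the lower end and everybody at the upper end. That needs the per-microlitre reading, which the labels rule out in practice. A unit is missing, but the limits are not impossible.
- **That an electronic screen would apply the wrong hemoglobin rule.** Section 4.3 describes the Epic report as finding people with psoriasis who attend certain clinics, with screening afterwards. It mentions no laboratory filter.
- **That everyone faces 120 ml of blood collection.** That total applies only to Group 1 participants with follow-up. Controls give at most 60 ml.

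**Conclusion.** The point holds as a wrong unit in an operative eligibility threshold, identical in both groups. Read literally, the hemoglobin limit of 0.009 g/dl excludes no one. This rests on the assumed adult range of about 3 to 18 g/dl and leaves a margin of more than 300-fold. The same wording in two separate lists makes a text-extraction artefact unlikely.

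The practical effect is probably small, because staff would most likely read a conventional unit. It would go too far to say that participants have no protection against bleeding risk, or that the whole criterion is inoperative: the word anemia, the bleeding-history exclusion and a workable reading of the platelet limits all remain. This is a minor correction, worth making because the limit bears on safety and the change is cheap.

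**What to change.** The sponsor should confirm the intended hemoglobin unit, correct it in 4.2 (item 6) and 4.3 (item 7), and carry the corrected limit into the screening form. As an editorial addition in the same amendment, state the unit for the platelet limits of 75 and 600 in both lists. If anyone has already been enrolled, record which hemoglobin unit was applied at screening.

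The cost is a two-line protocol correction and the matching form update. No new clinical threshold is proposed here; the intended limits are for the sponsor to state.

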4.3 Inclusion/Exclusion Criteria for Healthy Controls

Inclusion Criteria

Group 2: Healthy subjects without known psoriatic disease or cardiovascular disease

1. Age ≥ 18 & < 90
2. Able and willing to provide written informed consent for the study

Exclusion Criteria

2. Unable to speak Spanish or English
3. Active smoking (within the past year)
4. Autoimmune, rheumatologic or inflammatory disease which are not psoriasis or psoriatic arthritis
5. Known active cancer receiving treatment
6. Pregnancy
7. Anemia (hemoglobin < 9 mg/dl) or thrombocytopenia (Platelet count < 75), or thrombocytosis (Platelet count > 600)
8. A history of severe bleeding or bleeding disorders
9. Current medication use which interact with either aspirin or atorvastatin
10. Chronic kidney disease (CrCl < 30 ml/min)
11. Congestive heart failure
12. Currently taking aspirin or a statin.
13. NSAID use within the past 48 hours

Recruitment goals are listed in the schedule of assessments below. Both female and males will be recruited. Patients will be recruited from the outpatient general medicine, musculoskeletal/rheumatology and dermatology clinics at the NYU Faculty Group Practice (FGP) clinics including the Psoriasis, psoriatic arthritis ambulatory clinic, psoriasis and dermatology ambulatory care center and Bellevue Hospital Adult Clinics. We will also recruit from the Hospital for Joint Disease Psoriatic arthritis clinic which is staffed by NYU faculty. Patients fulfilling inclusion and exclusion criteria will be identified by their health care professional, who will obtain verbal consent for contact by a member of the research staff. Study brochures will also be left at the front desk of these practices in the event that subjects would like more information from study staff. Patients will be approached after their visit with the health care provider in the clinic setting. Subjects and healthy controls will also be recruited from posted fliers across the medical center. Additionally, subjects who have previously enrolled in any study (10-00607, S12-03123, S14-00531, s14-01418) by the co - PI ([name]) and who checked off the box that they may be contacted by a member of the study staff for potential enrollment will be included.

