Additional recruitment will be done through posted fliers and approved brochures at private dermatology offices with dermatology office staff permission. We will also recruit through social media postings including Craigslist, Facebook, psoriatic support groups and national psoriatic society patient

advocacy groups as well the NYU approved research match. The advertisement for these postings will contain the same content as noted on the IRB approved flyer. This social media advertisement will also include the health-union psoriasis advocacy website.

Working with MCIT and DataCore we will be using *Epic's Reporting Workbench tool* to identify potential subjects that have psoriasis and present to the dermatology FGP, arthritis or phototherapy clinics. We will screen these subjects and then if they meet study inclusion criteria and has agreed to be contacted for potential studies then they will be contacted. *Contact will be initiated using Epic and the patient portal, MyChart, via Epic's Research Recruitment functionality. The information used to send the MyChart message will be the same as that used for other study advertisements.*

Only subjects that have the capacity to consent will be asked to consent.

Vulnerable Population

We will not be enrolling any vulnerable populations.

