4.4 Informed consent

If a subject wishes to participate, a member of the research team will review the informed consent documents, answer any questions, and obtain written consent for participation in the study and obtain written consent for future analysis, contact, and sample storage. Subjects will be given a "Subject history form" to fill out asking for a complete medical history. They will also be given an appointment reminder sheet to bring with their consent form. They will bring the subject history form to their first baseline assessment appointment. Participants will consent to complete the baseline assessments (see table 1). Participants may opt to decline participation in any baseline assessment they feel uncomfortable with or time constraints do not allow. Follow-up assessments will be completed in those who agree to aspirin or atorvastatin usage for the longitudinal part of the analysis. Participation in follow-up assessment is not required for participation in the baseline assessment. The consent process will take place in private offices at the NYU FGP, CTSI, ambulatory care center, Seligman Center for Advanced Therapeutics and Bellevue adult clinics. Subjects will be given the opportunity to be contacted for future studies that they may qualify for as well. A member of the research team will conduct the baseline interview with the subject and review the clinical history, demographic information and medication use with the individual. All information including the consent will be kept under double lock and key at the PI's office in NYU Skirball 9th floor.

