4.5.2 Longitudinal component (Group 1 only)

After baseline assessment, those with moderate to severe psoriatic disease will be offered by the study physician randomly the opportunity for longitudinal follow up and to take either aspirin and/or atorvastatin. For 2 weeks +/- 4 days, 1/4th of the subjects enrolled will be offered 81mg of aspirin, 1/4th of the subjects enrolled will be offered atorvastatin 40mg, ¼ will be offered both aspirin and atorvastatin and 1/4th will be offered nothing. Participants will be given the opportunity to only participate in the baseline assessment and opt out of the opportunity to take aspirin and/or atorvastatin and longitudinal component.

Both aspirin and atorvastatin are routinely used and approved in medical practice for the primary prevention of coronary artery disease. These medications are frequently used in the psoriatic population based on national guidelines when a calculated cardiac risk score is elevated (considered at moderate to high risk of cardiovascular events). These medications will be obtained from the Tisch outpatient pharmacy. They will be stored and dispensed with CTSI oversight. A drug accountability and storage log will be kept as per NYU research protocol.

A follow up assessment will be planed (table 1) at 2 weeks +/- 4 days and will include repeat blood draw (60 ccs, for the use of platelet function testing, biospecimen collection) and repeated endothelial vein harvesting. The end of the study is considered when the subject completes the follow up assessment. All study drugs will be stopped at this time. If the subject wishes to continue the study drugs they will be referred to their primary medical provider for further management.

A subject will be able to opt out of any part of the follow up assessment they desire. If a subject agrees to be started on aspirin and/or atorvastatin for the longitudinal part of the analysis and therapy for psoriasis is planned by the referring provider, we will attempt to perform the longitudinal follow up prior to their starting medication. Participation in this study will not impact planned treatment of the subjects by their primary provider.

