All subjects may be asked to provide additional information about their medical history, update any interim history and provide additional samples as noted above. Health information will be monitored overtime by review of the medical chart. Additional questions may be asked by phone or during routine clinical follow-up, as appropriate.

Table 1. Patient Group		Baseline	Longitudinal Analysis	Follow-up
1 n = 40	Moderate to severe psoriatic disease	1) Blood 2) Endothelial vein harvesting 3) Vascular function imaging	Offered: 1) Aspirin 2) Atorvastatin	1) Blood 2) Endothelial vein harvesting 3) Additional medical history

				obtained
2 n = 10	Healthy Controls	1) Blood 2) Endothelial vein sampling 3) Vascular function imaging		1) Additional medical history obtained

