4.5.4 Endothelial cell harvesting

There will be a maximum of two time points for endothelial cell harvesting and biospecimen collection. Endothelial harvesting will take place either in the CTSI or in the NYU Seligman Center for Advanced Therapeutics. Both of these centers have access to nursing support and ancillary support staff including trained phlebotomists. All subjects will have their blood drawn and endothelial harvesting after informed consent and completion of the screening interview. If willing to the subjects will be preferably fasting > 4 hours and water intake is allowed. They will be in a reclined position with feet elevated. An angiocatheter ≤ 21 gauge will be inserted into a peripheral vein on the upper extremity using aseptic technique. A 0.021in. diameter J-shaped wire (Daig, Minnetonka, MN) or a 0.018in. diameter J-shaped wire (Arrow, Reading, PA) will be then advanced into the angiocatheter, to a distance of 4cm beyond the end of the angiocatheter. Angiocatheters and J shaped wire described above are routinely used for intravenous fluids and medication administration in this hospital. Venous endothelial cells will be scraped from the intimas of superficial forearm veins by repeated (3 times) insertion and removal of the wire. The distal portion of the wire will be transferred to a 50ml conical tube containing dissociation buffer (0.5% bovine serum albumin, 2 mM EDTA, and 100 microg/ml heparin in PBS, pH 7.4) and maintained at 4°C until study. Half of retrieved endothelial cells will be used for RNA extraction and a half for immunofluorescence.

The angiocatheter used will be a ≤ 21 gauge (typically 20 gauge) INSYTE autoguard IV catheter which is routinely used for clinical care, IV hydration and administration of medications. In this case we will using this angiocathter off label as a method to safety access the peripheral vein. This poses a non-significant risk for the device according to 21 CFR 812.3 (m) because: 1) There is NO implantation of the device. 2) This device will not be used to sustain human life and does not pose a serious risk to health or safety of the subject. 3) This device will not be used to diagnose, cure, mitigate or treat a disease. 4) This angiocatheter device is routinely used across the country in clinics and hospitals and does not pose a serious risk to health, safety or welfare of the subject.

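### Section 4.2 leaves out several known contraindications to aspirin or atorvastatin, and no complete written rule turns the patient's history into drug eligibility before the random offer in 4.5.2.

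*Combined protocol and SAP*

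**What the plan says.** Section 4.2 lists 12 exclusions for psoriatic patients. Those that bear on drug safety are pregnancy, low hemoglobin or abnormal platelet count, severe bleeding or a bleeding disorder, "Current medication use which interact with either aspirin or atorvastatin", CrCl below 30 ml/min, heart failure, current aspirin or statin use, and NSAID use in the last 48 hours. Exclusion 3 removes other autoimmune, rheumatologic or inflammatory disease.

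Under section 4.5.2, after baseline, patients with moderate to severe disease "will be offered by the study physician randomly the opportunity for longitudinal follow up and to take either aspirin and/or atorvastatin". A quarter each are offered aspirin 81 mg, atorvastatin 40 mg, both or nothing, for about 2 weeks. Patients may "opt out of the opportunity to take aspirin and/or atorvastatin and longitudinal component".

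Several steps could bring a contraindication to light:
- Recruitment text in 4.3: "Patients fulfilling inclusion and exclusion criteria will be identified by their health care professional". For patients found through Epic it says "We will screen these subjects and then if they meet study inclusion criteria", followed by contact if they have agreed to it.
- Section 4.4: patients complete a medical history form, and staff "review the clinical history, demographic information and medication use with the individual".
- Section 4.5.2: "Health information will be monitored overtime by review of the medical chart".
- Section 4.5.4: sampling takes place "after informed consent and completion of the screening interview".
- Section 11.1: significant abnormalities at screening are recorded as preexisting conditions.

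Section 5 names ulcers and bleeding as aspirin harms, and hepatotoxicity and myositis as atorvastatin harms. It does not mention allergy.

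**The concern.** Section 4.2 is clearly meant to keep patients away from drugs that could harm them, but it does so only in part. A patient with an ulcer that has never bled severely, fatty or alcoholic liver disease, past statin myopathy or aspirin allergy can meet every written criterion and enter the draw. If the draw gives the unsuitable drug, the patient either takes it or has it withheld once the option is known. The week-1 call and week-2 visit in section 11.5 can pick up harm only after exposure has begun. Under section 11.4 a serious adverse event would interrupt the study for review. What is at stake is mainly the safety of individual patients, and secondarily an avoidable interruption in a small pilot.

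**Working it through.** **Text check.** Each condition is set against the nearest exclusion in 4.2 and the harms in section 5.

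| Condition | Nearest exclusion | Covered? | Harm named in section 5? |
|---|---|---|---|
| Active peptic ulcer | 7, severe bleeding or bleeding disorder | Only if it bled severely | Yes, ulcers (aspirin) |
| Active liver disease | 3, autoimmune or inflammatory disease | Autoimmune yes; fatty, alcoholic or drug-related not clearly; infectious hepatitis unclear | Yes, hepatotoxicity (atorvastatin) |
| Prior myopathy | 3 | Inflammatory yes; non-inflammatory or statin-related no | Yes, myositis (atorvastatin) |
| Allergy or past intolerance | 8, interacting drugs; 11, current use | No | Allergy not named |

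No other section supplies the missing criteria. The steps listed under what the plan says collect information, but none states what a finding does to drug eligibility. In section 11.1 an abnormality found at screening feeds adverse-event recording only. The opt-out in 4.5.2 is the patient's choice, not a medical rule. Section 4.3 also allows recruitment by flier and social media, so a treating clinician does not filter every patient.

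**Chance of drawing an unsuitable drug.** Four equal options (4.5.2):
- Unsuitable for one drug: 2 of 4 options contain it, 2/4 = 50%.
- Unsuitable for both: 3 of 4 contain at least one, 3/4 = 75%.

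**Illustrative counts.** Assumptions: a share p is unsuitable for each drug, independently; all 40 enter the draw, 10 per option; nobody opts out and the physician does not intervene. The value of p is not in the documents.

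- Affected after the draw = 10p + 10p + 10(1 − (1 − p)²) + 0. At p = 0.05: 0.50 + 0.50 + 0.975 = 1.975.
- Baseline-only if screened before the draw = 40(1 − (1 − p)²). At p = 0.05: 40 × 0.0975 = 3.9.
- Left per arm = 10(1 − p)².
- Enrolment needed to keep 40 in the draw = 40/(1 − p)², rounded up.

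| p | Affected after draw | Baseline-only under the fix | Left per arm | Enrolment for 40 in draw |
|---|---|---|---|---|
| 2% | 0.8 | 1.6 | 9.6 | 42 |
| 5% | 2.0 | 3.9 | 9.0 | 45 |
| 10% | 3.9 | 7.6 | 8.1 | 50 |

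Independence matters. If the same patients are unsuitable for both drugs, then at 5% the affected count is 30 × 0.05 = 1.5 and the baseline-only count is 40 × 0.05 = 2.0.

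**Power, used only to price the fix.** Section 9 gives 74% for n = 10 per group, d = 0.8, alpha 0.05, sidedness not stated. A paired t-test with the noncentral t gives 75.4% one-sided, within 2 points of the plan, and 61.6% two-sided. The one-sided reading is the closer. With n = 9 and n = 8, one-sided power is 70.7% and 65.3%; two-sided it is 55.9% and 49.6%.

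**The case against.** The strongest reply is that the sequence is largely in place. The offer follows baseline, a physician makes it, the history form is due by then, and the drugs are dispensed with CTSI oversight. Exposing a patient with a disclosed contraindication would require the physician to overlook it. The forms themselves are not visible in the public text and may ask about allergy, ulcer and liver disease. The drugs are also given at ordinary doses for only about 2 weeks. All of this stands, and it lowers the likely exposure. It does not supply a rule that says what counts as unsuitable, or that this is decided before the option is known.

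It can also be said that section 5 lists side effects, not contraindications, and never mentions allergy. That is correct: treating pre-existing disease or allergy as a reason to exclude is ordinary clinical reasoning, not a statement in the plan.

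Stronger readings that the documents do not support:
- A reader might infer that the plan has no rule on drug suitability at all. Exclusions 3, 5 to 9, 11 and 12 settle a good part of it before any offer. What is missing is a complete rule.
- A reader might infer that one avoidable serious reaction would end the trial. Section 11.4 provides for interruption and a search for the cause, and the same rule applies after more than 5 adverse events of any kind.
- A reader might infer that withholding after the draw biases the treatment results. It would remove patients only from options containing that drug, but the only test Aim 3 specifies is the paired t-test, and voluntary opt-out already permits similar selection.
- A reader might take the counts as expected harms. They count patients who draw an option, under an assumed prevalence; no probability of injury can be derived from the documents.

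**Conclusion.** The gap holds as a limited patient-safety point: four kinds of known contraindication are wholly or partly outside the exclusions, and the protocol does not require suitability to be settled before the draw. The figures that follow from the plan alone are the 2/4 and 3/4 chances. The 0.8 to 3.9 affected patients of 40 rest on an assumed 2% to 10% per drug and on independence. They also assume full participation without clinical intervention, so real exposure at a given prevalence should be lower. The finding concerns the protocol text only, since the consent and history forms cannot be seen. It is a minor improvement, worth making because it is cheap.

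**What to change.** For the longitudinal component only, add to 4.2 and 4.5.2 exclusions for known or documented active peptic ulcer, active liver disease, prior myopathy, allergy to aspirin or a statin, and intolerance that led to stopping either drug. The last phrase keeps mild heartburn or muscle soreness from excluding people. Check these from the history form and interview already planned in 4.4, and have the study physician record the result before the option is drawn. A patient unsuitable for either drug stays baseline-only and still contributes to Aims 1 and 2.

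The cost is a short amendment and a checklist, with no new visit or test. Because someone unsuitable for only one drug also leaves the draw, the fix removes more patients than would be affected after it: about 1.6, 3.9 or 7.6 of 40 at 2%, 5% or 10%. Without extra recruitment, arms shrink to about 9.6, 9.0 or 8.1, and one-sided paired power falls from 75% with 10 to 71% with 9 or 65% with 8. Keeping 10 per arm would need about 42, 45 or 50 psoriatic patients. Undiagnosed disease would still be missed, and opt-out after the offer remains possible.
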